Improving Aging in Place for Older Adults Living in Subsidized Housing

NCT04212442

July 1, 2020

Aim 3: Determine the feasibility and preliminary effectiveness of the adapted Function-Focused Care intervention in subsidized housing residents at high risk for nursing home admission. We will conduct a 2-month pilot test of the adapted Function-Focused Care intervention in 15 subsidized apartment buildings for older adults. We will use a pre-to-post study design to examine the change in outcome measures from baseline to 2 months. Implementation outcomes will include feasibility and acceptability. Preliminary effectiveness outcomes will include resident function (primary outcome), with secondary outcomes of quality of life and health care utilization. Because function declines over time, our design will incorporate a waitlist control, in which half of the sites are cluster randomized to receive the intervention in months 0-2 while the other sites are randomized to receive usual care. The waitlist sites will then receive the intervention in months 2-4. The waitlist period will provide a baseline rate of functional decline that will serve as a comparison for functional outcomes (see Figure 3 for study flow).

Study setting and population: We will pilot the intervention in 15 subsidized apartment buildings for older adults.

Eligibility: Residents living at any of the sites will be invited to participate. If a resident wishes to participate but does not pass consent verification,⁶⁷ they will be asked to sign an assent to participate, and a proxy will be contacted to complete the consent process. Residents will receive sequential \$50 incentives for participation at baseline, 3, and 6 months (i.e., up to \$150 total).

[figure not shown]

Figure 3.

resident-family caregiver dyads, among residents who have such support.

A research Function-Focused Care Nurse will coordinate and implement the intervention with support from our interdisciplinary research team. The nurse will receive extensive training in the intervention. This will include a 1-week in-person training with [name] and her team at the University of Maryland in Year 1, followed by weekly web-based training during the first 6 months of Year 2 and as-needed check-ins in Years 2 and 3. Based on the successful implementation model for assisted living,³⁵ the nurse will work with each site 16 hours per week for the first 3 months of the intervention and 8 hours per week for the next 3 months. To ensure that the intervention can be sustained over time, we will work with each site to identify a staff “champion” who will work with the nurse to learn how to maintain this approach. Working with the champion, the nurse will implement the 4 steps of the intervention (Table 2). As noted above, the approach for each step may be adapted based on stakeholder feedback, e.g., to incorporate family caregivers. Steps will be implemented sequentially and continue throughout the intervention, including ongoing mentorship and motivation for residents and caregivers. This will include observing caregiver performance, giving positive encouragement for providing Function-Focused Care, and reinforcing benefits of the intervention. Mentorship will occur in-person.

Table 2. Component	Description of the intervention
I: Environmental and policy assessments	Site champion works with research nurse to complete assessments using standard evaluation forms. Findings are used to identify and recommend feasible interventions to alter the environment, policy, and procedures to optimize resident function and physical activity (e.g., make pleasant walking areas)
II: Education	Research nurse educates housing staff (e.g., service coordinators), residents, and families in principles of Function-Focused Care (FFC), using established materials and adult learning techniques.
III: Establishing goals	Research nurse works with residents to complete Capability Assessments/Goal Attainment Forms with eligible residents. Goals established based on assessments and resident input.
IV: Mentoring and motivating	Research nurse works to motivate residents to participate in FFC throughout study period by using evidence-based approaches (e.g., observing performance of caregivers and providing one-on-one mentoring to incorporate FFC into routine care; providing positive reinforcement for incorporating FFC)

Waitlist control: At the waitlist control site, residents will be screened for risk of nursing home admission and

enrolled as described in Aim 2. Residents will be referred for whatever services are customary per usual facility protocols based on results of these screenings, but for the next 2 months, will not be enrolled in the Function-Focused Care intervention.

Outcome measures: Outcomes are shown in Table 3. Measures will be collected at baseline and 2 months at both sites, and at 4 months at the waitlist control site (i.e., 2 months after intervention initiation at the control site). Measures correspond to the outcome domains assessed in the original Function-Focused Care trial³⁵ and were selected because they have well-established validity and reliability. Measures of feasibility will include standard measures of recruitment, retention, and refusal. We will assess intervention fidelity once per resident by evaluating home care workers during care interactions using a fidelity checklist.⁷⁹ Acceptability for residents, workers, and leaders will be assessed in both sites using similar approaches to Aim 2.⁷⁷

Table 3. Outcomes	Data source/measure
Feasibility	
Recruitment, retention, and refusal rates; intervention fidelity	Facility observations; Restorative Care Checklist ⁷⁹
Acceptability	
Satisfaction, usability, burden	Stakeholder interviews
Resident outcomes	
Function (co-primary outcomes)	SPPB, ⁸⁰ Yale ADL scale ⁶⁸⁻⁷¹
Quality of life, depression	QOL-AD, ⁸¹ PHQ-9 ⁸²
Health care utilization	No. hospital/nursing home admissions; length of stay
Adverse events	No. falls, fall-related injuries
Beliefs about function and physical activity	Self-efficacy/Expectations for Functional Activity Scales ⁸³⁻⁸⁷
Caregiver outcomes	
Knowledge of intervention	11-item scale ⁸⁸
Self-efficacy and outcome expectations	Self-efficacy/Expectations for Restorative Care Activities ⁸⁷
Job satisfaction	Job Attitude Scale ⁸⁹
Family caregivers: QOL, depression, caregiver burden	EQ-5D, ⁹⁰ PHQ-9, ⁸² brief Zarit Caregiver Burden scale ⁹¹

Resident outcomes include key factors that contribute to aging in place, including a primary outcome of functional status and secondary outcomes of quality of life, depression, and health care utilization. We will measure function using 2 measures. The Short Physical Performance Battery (SPPB) is an objective measure of lower extremity functioning in older adults which has excellent reliability, validity, and responsiveness (range, 0-12 points).^{80,92} We will also measure self-reported ability to perform 8 ADLs using the Yale ADL scale (range, 0-16).⁶⁸⁻⁷¹ We will assess quality of life using the Quality of Life in Alzheimer's Disease (QOL-AD) scale⁸¹ and depression using the Patient Health Questionnaire (PHQ-9).⁸² Health care utilization will be assessed by self-report. Other outcomes will include adverse events and attitudes about function and physical activity (see Table 3).⁸³⁻⁸⁷ Home care

worker outcomes will include knowledge⁸⁸ and attitudes about Function-Focused Care⁸⁷ and job satisfaction.⁸⁹ For family caregivers, outcomes will include quality of life,⁹⁰ depression,⁸² and caregiver burden.⁹¹

Analysis plan and power calculation: We will analyze measures of feasibility using similar methods to Aim 2. We will define the intervention as feasible if residents complete $\geq 75\%$ of checklist items. For other outcomes, we will assess change from baseline to 2 months and compare the changes between intervention and waitlist groups. For continuous outcomes, the change will also be continuous; for dichotomous outcomes, the change can be defined as a four-category variable (0-0, 0-1, 1-0, and 1-1 for pre and post outcomes). We will then compare the change between intervention and waitlist groups using the t-test or Wilcoxon signed rank sum test for continuous variables and Chi-square or Fischer's exact test for dichotomous variables.

Because this is a pilot feasibility study, the sample size need only be large enough to determine key parameters such as recruitment, retention, and refusal rates. Given the pool of potential participants, we are confident that we can recruit enough participants to not only determine feasibility but also determine point estimates and standard deviations for projected sample size for a follow-up randomized controlled trial. We plan to recruit a total of 70 participants in the overall study. To estimate preliminary effect sizes, the mean scores for continuous outcomes or proportions for dichotomous outcomes will be compared among participants in the intervention vs. waitlist control conditions. If we assume that the correlation between pre and post continuous measures from baseline to 6 months is 0.8, then the SD for the change is 0.6 SD for the continuous measures. With 70 residents, we will have 80% power (2-sided alpha of 0.05) to detect a 0.66 SD change in the mean of continuous measures from baseline to 2 months, assuming a 20% dropout. Thus, for our primary outcomes, we should have sufficient power to detect a mean 1.78-point increase in SPPB score (SD~2.7)⁹¹ and a mean 1.45-point increase in ADL/IADL score (SD~2.2).⁷⁶

Potential problems and alternative approaches: Potential problems include staff turnover, resident loss to follow-up, and a relatively limited sample size and follow-up period. We will train new staff and champions and use best practices to minimize loss to follow-up, including obtaining multiple types of contact information at baseline and providing sequential incentives for participation. Also, our implementation protocol will incorporate stakeholder input on barriers and facilitators to implementation identified in Aim 1. Although this pilot study has a limited sample size, it will provide preliminary data to support a definitive R01-level study.

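### SPPB and Yale ADL are compared as unadjusted 2-month changes; adjusting for each resident's baseline score, with the slope estimated within buildings, would give a small precision gain

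*Combined protocol and SAP*

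**What the plan says.** All references are to the combined protocol and SAP.

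- **Outcome measures.** SPPB and the Yale ADL scale are co-primary. "Measures will be collected at baseline and 2 months at both sites", so each resident has a baseline score in either arm.
- **Analysis plan and power calculation.** For outcomes other than feasibility, "we will assess change from baseline to 2 months and compare the changes between intervention and waitlist groups". The method follows: "We will then compare the change between intervention and waitlist groups using the t-test or Wilcoxon signed rank sum test for continuous variables". The sample-size paragraph adds that means will be compared between conditions to estimate preliminary effect sizes. No covariate, regression model or baseline adjustment is named anywhere.
- **Sample-size paragraph.** It assumes that "the correlation between pre and post continuous measures from baseline to 6 months is 0.8" and concludes: "then the SD for the change is 0.6 SD for the continuous measures". One purpose of the pilot is to "determine point estimates and standard deviations for projected sample size for a follow-up randomized controlled trial".
- **Aim 3, opening paragraph.** Allocation is by building: "half of the sites are cluster randomized to receive the intervention in months 0-2".

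**The concern.** Subtracting the baseline fixes its slope at 1. If baseline and 2-month scores have equal SDs and correlation r, the slope that minimises the variance is r. A change score therefore over-corrects whenever r is below 1 and carries some avoidable noise. The baseline scores are being collected anyway, so the gain needs no extra data.

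The stake is modest. The pilot's effect estimates are meant to inform a follow-up trial, and a somewhat tighter estimate of the between-arm difference serves that purpose. The observed 2-month correlation would serve it too, because the plan's only correlation is for 6 months.

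**Working it through.** **Inputs.** From the documents: 70 residents, 20% dropout, two-sided alpha 0.05, 80% power, r = 0.8, SPPB SD 2.7, ADL SD 2.2, 15 buildings. Assumed: 28 completers per arm (70 × 0.8 = 56; the documents give no split of residents), equal SDs at baseline and 2 months, 7 versus 8 buildings with 3 or 4 completers each, ICC 0 to 0.10, and a building-level correlation equal to r.

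**The plan's own figure.** The plan states a detectable 0.66 SD (0.66 × 2.7 = 1.78 SPPB points; 0.66 × 2.2 = 1.45 ADL points). With 28 per arm, (1.96 + 0.84) × SD × sqrt(2/28) gives 0.449 SD for an SD of 0.6 and 0.474 SD for 0.632. The 0.66 is not reproduced. That is a separate matter and is not used here.

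**SDs at r = 0.8.**
- Change: sqrt(2 × (1 − 0.8)) = sqrt(0.4) = 0.632.
- 2-month score adjusted for baseline: sqrt(1 − 0.8²) = sqrt(0.36) = 0.600.
- Variance ratio: 0.36/0.40 = 0.90. Estimating the slope from 56 residents costs a factor of about 1 + 1/52, so the net ratio is 0.917.

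**Residents treated as independent, r = 0.8 (t-based).**

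| | Change (54 df) | Adjusted (53 df, slope cost included) |
|---|---|---|
| Standard error, SD units | 0.632 × sqrt(2/28) = 0.169 | 0.600 × sqrt((2/28) × (1 + 1/52)) = 0.162 |
| 95% CI half-width, SD units | 0.339 | 0.325 |
| Same, SPPB points (× 2.7) | 0.92 | 0.88 |
| Detectable difference, 80% power, SD units | 0.482 | 0.462 |
| Same, SPPB points (× 2.7) | 1.30 | 1.25 |
| Same, ADL points (× 2.2) | 1.06 | 1.02 |
| Power at 0.482 SD | 80% | 83% |

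**Other values of r (assumed).** At the effect for which the change score has 80% power, the adjusted analysis has 85% at r = 0.7, 82% at 0.85, 81% at 0.9 and 80% at 0.95.

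**With 15 buildings.** Simulated power (%) at ICC 0 / 0.05 / 0.10:

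| Analysis | r = 0.8, difference 0.482 SD | r = 0.9, difference 0.341 SD |
|---|---|---|
| Change, building means, 13 df | 74.3 / 69.2 / 64.2 | 74.3 / 69.3 / 64.0 |
| Within-building slope, building means of residuals, 13 df | 77.6 / 72.7 / 67.8 | 75.5 / 70.4 / 65.1 |
| Random building effect (REML), baseline covariate, 13 df | 75.5 / 70.7 / 66.8 | 72.3 / 68.0 / 64.0 |
| Slope from the 15 building means, 12 df | 74.7 / 69.5 / 64.8 | 72.6 / 67.5 / 62.3 |

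Against the change comparison in the top row:
- The within-building slope gains 3.3 to 3.6 points at r = 0.8 and 1.1 to 1.2 at r = 0.9. Its Type I error is near 5%.
- The random-effect model gains 1.2 to 2.6 points at r = 0.8. At r = 0.9 it ranges from 2.0 points lower to no difference. At r = 0.8 its Type I error is 2.7 to 3.8%, so it is conservative.
- A slope from building means gains 0.3 to 0.6 points at r = 0.8 and loses 1.7 to 1.8 at r = 0.9.

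At r = 0.8, for the within-building version, the gain is 4.2 points if the building-level correlation is 0.6 and 2.7 to 3.2 points if it is 0.89.

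**Baseline imbalance.** Given an imbalance B, the change contrast is shifted by (1 − r) × B. At r = 0.8 and B = 0.25 SD this is 0.2 × 0.25 = 0.05 SD. The variance difference between the two analyses, before slope cost, is (2/28) × (0.40 − 0.36) = 0.00286. The variance of the shift is (1 − r)² × Var(B) = 0.04 × (2/28) = 0.00286. They are the same quantity, so the protection against imbalance is the precision gain seen conditionally and not a second benefit.

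**The case against.** The strongest case is that this is a preference. The change contrast is unbiased under randomization, the pilot is sized for recruitment, retention and refusal rates, and change fits a design in which the waitlist supplies the background rate of decline. At the plan's own 0.66 SD target, power ignoring clustering is 97.4% for change and 98.4% adjusted, and the SPPB half-width narrows by about 0.04 points on a 0 to 12 scale. All of this is correct, and it limits the point to an optional improvement. It does not remove it: the plan commits to effect estimates for a later trial, and the gain needs no new data.

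A second objection is that the gain depends on r and on the method. This also stands. The random-effect model shows no gain at r = 0.9, and a slope from building means loses power there.

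A third is that most of the rewriting belongs to handling the clustering. That is fair; once a clustered analysis is written, baseline is one added step. The plan's rank-test option for two bounded scales is also not covered by this calculation, which concerns means.

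A reader might infer that 0.6 SD is an arithmetic error. The documents do not establish that: 0.632 rounds to 0.6, and 0.600 is exactly the adjusted residual SD at r = 0.8. The wording is ambiguous.

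**Conclusion.** The point holds as a small, optional precision gain. At r = 0.8 the variance falls by about 8% with residents treated as independent. With 15 buildings and a within-building slope, power rises by 3 to 4 points. The gain is about 1 point at r = 0.9 and negligible near 0.95. These figures rest on 28 completers per arm, equal SDs at both visits, an ICC of 0 to 0.10 (the documents give none), and a correlation that the plan states for 6 months. The 2-month correlation is unknown, and if it is higher the gain is smaller.

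A reader might take this to mean that the planned comparison is biased or invalid. It is not: over repeated randomizations the change contrast estimates the same between-arm difference. Nor does adjustment repair the 0.66 SD figure or the absence of clustering from the named tests; both are separate and larger matters.

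**What to change.** 1. For SPPB and Yale ADL, make the primary comparison the 2-month score adjusted for the resident's own baseline score. Estimate the slope from residents within buildings, then compare the building means of the residuals between arms.
2. A random-building model with baseline as a covariate is an acceptable alternative, stated as conservative here and possibly without gain at high r. Do not estimate the slope from the 15 building means.
3. Report the adjusted difference with its 95% CI, and use it as the preliminary effect size. Report the observed 2-month correlation for planning the next trial, and keep mean change by arm as description.
4. In the sample-size paragraph, state whether 0.6 SD is the SD of the change (0.632 at r = 0.8) or the baseline-adjusted residual SD (0.600), and note that r = 0.8 is a 6-month assumption.

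**Cost.** One or two sentences in the analysis plan, one clarified phrase in the sample-size text, and no new data. Estimating the slope costs about 2% of variance, and there may be little or no gain if the 2-month correlation is very high.

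### For any outcome analysed as dichotomous, a baseline-adjusted comparison of 2-month status would serve the pilot's estimation aim better than an omnibus test on four pre/post patterns (minor)

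*Combined protocol and SAP*

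**What the plan says.** The first paragraph of Analysis plan and power calculation sets the comparison: "we will assess change from baseline to 2 months and compare the changes between intervention and waitlist groups". For a dichotomous outcome it offers this coding: "the change can be defined as a four-category variable (0-0, 0-1, 1-0, and 1-1 for pre and post outcomes". The between-arm comparison is then made "using the t-test or Wilcoxon signed rank sum test for continuous variables and Chi-square or Fischer's exact test for dichotomous variables". The patterns are not ordered, baseline status is not adjusted for, and no effect measure or interval is attached to the test.

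The second paragraph, on sample size, covers estimation separately: "To estimate preliminary effect sizes, the mean scores for continuous outcomes or proportions for dichotomous outcomes will be compared among participants" in the two conditions. It also gives the aim of the estimates, which is to "determine point estimates and standard deviations for projected sample size for a follow-up randomized controlled trial". It does not say whether the proportions are of 2-month status, of improvement or of something else, or how baseline status is used.

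Table 3 lists scales, counts and length of stay, and labels none of them dichotomous. The power statement covers continuous measures only.

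**The concern.** A test on four unordered patterns asks whether the arms differ in any way at all. Part of what it measures is whether the arms started alike, and it cannot tell improvement from deterioration. A pilot whose product is estimates for a later trial needs a directional quantity with an interval. If an outcome is analysed this way, the reported p-value could miss a consistent improvement that a one-df comparison on the same data would show. The proportions comparison meant to supply the estimate would also remain undefined. If that comparison were read as an unadjusted contrast at 2 months, it would be exposed to chance baseline imbalance, which is a real possibility with about 28 residents per arm.

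**Working it through.** **Plan's own figure.** None exists for dichotomous outcomes. The 0.66 SD detectable change concerns continuous measures and is not used here.

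**Inputs.** From the plan: 70 residents and 20% dropout, so 70 × 0.8 = 56 completers; two-sided alpha 0.05. Assumed: 28 completers per arm, individual-level data (building clustering left out), and all prevalences and transition rates, since the documents give none.

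**1. What the test contains.** A 2 × 4 table has (2 − 1)(4 − 1) = 3 df. One compares baseline status between arms, one compares transitions from 0, and one compares transitions from 1. (Fisher's exact test has no df, but it is equally omnibus.)

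**2. Illustrative table**, constructed with no baseline gap; 1 is the favourable state.

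| Arm | 0-0 | 0-1 | 1-0 | 1-1 | Baseline | 2 months |
|---|---|---|---|---|---|---|
| Waitlist | 12 | 2 | 6 | 8 | 14/28 = 50% | 10/28 = 36% |
| Intervention | 8 | 6 | 2 | 12 | 14/28 = 50% | 18/28 = 64% |

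- Four-pattern chi-square: expected counts are 10, 4, 4 and 10 in each arm, so the statistic is 2 × (4/10 + 4/4 + 4/4 + 4/10) = 5.60 on 3 df, p = 0.13. Fisher's exact p = 0.17. Swapping the arms leaves both unchanged.
- Likelihood-ratio split: 5.80 = 0 (baseline) + 2.90 (from 0) + 2.90 (from 1).
- Mantel-Haenszel stratified by baseline status: observed minus expected is 6 − 4 = 2 in one stratum and 12 − 10 = 2 in the other. Each variance is 14 × 14 × 8 × 20 / (28² × 27) = 1.48. Then z = 4/√2.96 = 2.32, p = 0.020. With continuity correction, z = 3.5/√2.96 = 2.03, p = 0.042.
- Risk difference: 4/14 = 0.286 in each stratum, so 0.286 pooled. Its SE is 0.1145, giving a 95% CI of 0.061 to 0.510.

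**3. Size under no effect.** P(0 to 1) = 0.15 and P(1 to 1) = 0.80 in both arms, baseline prevalence 20% to 50%, 10,000 runs each. Rejection rates: four-pattern chi-square 3.9% to 4.1%; Fisher 4.7% to 5.0%; Mantel-Haenszel 4.6% to 5.0%; Mantel-Haenszel with continuity correction 1.6% to 1.9%.

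**4. Power** at baseline prevalence 40%, 6,000 runs each:

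| P(0 to 1), waitlist to intervention | P(1 to 1), waitlist to intervention | Chi-square | Fisher | Mantel-Haenszel |
|---|---|---|---|---|
| 0.08 to 0.30 | 0.50 to 0.85 | 50.6% | 51.5% | 69.3% |
| 0.10 to 0.30 | 0.60 to 0.85 | 32.3% | 32.9% | 50.1% |
| 0.15 to 0.35 | 0.60 to 0.80 | 24.4% | 25.0% | 39.0% |
| 0.15 to 0.40 | 0.70 to 0.85 | 29.4% | 30.7% | 43.4% |

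Over prevalences of 30% to 50%, Mantel-Haenszel exceeds chi-square by 14.0 to 20.0 points and Fisher by 12.7 to 18.8. The continuity-corrected version exceeds chi-square by only 1.9 to 7.1.

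**5. Where the gain disappears or reverses.**
- Effect in one starting state only (prevalence 40%), chi-square against Mantel-Haenszel: 32.2% vs 33.3%, 27.2% vs 25.1%, 21.8% vs 22.5%.
- Opposite effects by baseline status: with prevalence 50%, P(0 to 1) 0.10 to 0.45 and P(1 to 1) 0.90 to 0.55, power is 70% vs 5%. With prevalence 40%, 0.15 to 0.40 and 0.85 to 0.55, it is about 43% vs 5%.

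**6. Baseline imbalance.** In the null runs of step 3 a baseline gap of 20 points or more arose in 6.6% to 13.8% of trials. Within those trials the rejection rates were 17.3% to 26.3% for the four-pattern chi-square, 15.8% to 22.8% for unadjusted 2-month proportions, and 3.5% to 5.8% for Mantel-Haenszel.

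**The case against.** The case for leaving the text alone is substantial.

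- **No identified target.** No outcome is labelled dichotomous, the coding is only permitted, and no power is claimed for it. This stands, and it keeps the point minor. The plan nevertheless writes a rule for such outcomes in two places, and that rule should serve the stated aim.
- **The estimate is assigned elsewhere.** A reader might infer that the plan has no effect estimate for dichotomous outcomes, or that its two paragraphs contradict each other. Neither is supported: the second paragraph does plan a comparison of proportions. What is missing is which proportions and how baseline status enters.
- **The test is valid and answers whether change differs.** A reader might infer inflated type I error. Overall size is nominal or slightly below, so that does not hold. The excess under a large baseline gap is conditional on the gap, and unadjusted proportions share it.
- **The stratified test is not uniformly better.** This stands. It answers a narrower question and is nearly blind to effects of opposite sign. The size of its advantage also depends on assumed rates, and the illustrative table was chosen to be symmetric. Another table (waitlist 10/3/9/6, intervention 10/9/3/6) gives chi-square p = 0.112 and Mantel-Haenszel p = 0.065, so neither is significant. The stratified analysis still supplies a direction and a risk difference of 0.25.
- **Clustering dominates.** Fifteen buildings are randomized, and the p-values and interval above ignore this. They illustrate the contrast between tests and are not results this trial could report.

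The test name in the continuous part merges the paired signed-rank and two-sample rank-sum tests. A reader might infer that a paired test is planned. The text compares two groups, so the rank-sum test is evidently meant, and this is editorial only.

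**Conclusion.** This is a cheap improvement of minor weight. The four-pattern test is valid apart from clustering, but it carries no direction and spends a df on something the intervention cannot change. The comparison of proportions that should supply the estimate is left undefined. The case for a baseline-adjusted estimate with an interval rests on the pilot's stated aim and does not depend on the power figures. Those figures are conditional on assumed rates, 28 per arm and no clustering: a gain of about 14 to 20 points when both transitions improve, 2 to 7 with a continuity correction, none when one starting state carries the effect, and a large loss when effects run in opposite directions. The t-test on the SPPB and Yale ADL change scores is not touched.

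**What to change.** In the first paragraph of Analysis plan and power calculation, state that for any outcome analysed as dichotomous, 2-month status will be compared between arms stratified by or adjusted for baseline status, with a risk difference or odds ratio and its 95% CI. In the second paragraph, state that this is the comparison of proportions meant there. Keep the four-pattern table by arm as description, so that effects running in opposite directions by baseline status stay visible. The interval and p-value must follow whatever method the plan adopts for building randomization, which is a separate matter. As an editorial correction, name the Wilcoxon rank-sum (Mann-Whitney) test.

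Cost: one sentence and one test name in the first paragraph and one sentence in the second. The baseline and 2-month data are already planned, so no new data and no additional residents are needed.

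### Buildings are randomized, but the between-group tests and the power text treat residents as independent, so with any positive within-building correlation of change the t-test rejects more often than 5%

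*Combined protocol and SAP*

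**What the plan says.** The opening paragraph of Aim 3 describes a waitlist design across 15 subsidized buildings and sets out the allocation: "half of the sites are cluster randomized to receive the intervention in months 0-2 while the other sites are randomized to receive usual care". The building is therefore the unit of randomization, with 8 against 7 if the split is as even as possible.

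Under Analysis plan and power calculation, the change from baseline to 2 months is compared between arms: "We will then compare the change between intervention and waitlist groups using the t-test or Wilcoxon signed rank sum test for continuous variables". Dichotomous outcomes are turned into a four-category change and compared by chi-square or Fisher's exact test. The power statement reads: "With 70 residents, we will have 80% power (2-sided alpha of 0.05) to detect a 0.66 SD change in the mean of continuous measures", with 20% dropout assumed.

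The document contains no ICC, design effect, mixed model, GEE, robust standard error or building-level analysis. The reference back to the methods of Aim 2 covers only the feasibility measures.

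Outcome measures also describes the sites differently: "Measures will be collected at baseline and 2 months at both sites, and at 4 months at the waitlist control site". Read literally, that is one building per arm, not 15 buildings.

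**The concern.** When buildings are randomized, the variance of the difference between arms has a between-building part. A test that treats residents as independent omits part of it. If the ICC of the 2-month change is positive, p-values are too small and intervals too narrow for the co-primary comparison.

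The document gives some reason to expect a positive ICC. In the waitlist arm, care depends on the facility: "Residents will be referred for whatever services are customary per usual facility protocols based on results of these screenings". The intervention works partly through each building's environment, policies and champion (Table 2). It also gives reasons to expect a small ICC. Mentoring is one-on-one, and goals are individual: "Goals established based on assessments and resident input".

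A second consequence concerns what the pilot is for. It is meant to "determine point estimates and standard deviations for projected sample size for a follow-up randomized controlled trial". If the follow-up trial also randomizes buildings, its sample size needs an ICC, and the plan does not say one will be estimated.

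**Working it through.** **Inputs from the document.** 15 buildings (Aim 3). From Analysis plan and power calculation: 70 residents, 20% dropout, pre-post correlation 0.8, SD of change given as 0.6 SD, two-sided alpha 0.05, 80% power, detectable change 0.66 SD.

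**Derived.** Completers: 70 × 0.8 = 56, taken as 28 per arm. Mean per building: m = 56/15 = 3.73. SD of change: √(2(1 − 0.8)) = 0.632, which the plan rounds to 0.6.

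**Assumed.** ICC of change 0.01 to 0.20. Completers per building in the two arms:
- near-equal: 4,4,4,4,3,3,3,3 against 4,4,4,4,4,4,4 (coefficient of variation, CV, 0.12)
- uneven: 8,6,4,3,2,2,2,1 against 9,6,5,3,2,2,1 (CV 0.65)

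**The plan's own figure.** A two-sample t-test with 28 per arm and no clustering has 80% power for 0.457 SD (SD of change 0.6) or 0.482 SD (0.632). The stated 0.66 SD does not reproduce. That is a separate error and carries no weight here.

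**Type I error.** The design effect is DE = 1 + ((1 + CV²)m − 1) × ICC. With m = 3.73:
- CV taken as 0: DE = 1 + 2.73 × ICC
- CV 0.65: 1.4225 × 3.73 − 1 = 4.31, so DE = 1 + 4.31 × ICC

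For equal sizes, the approximate true error of a nominal 5% test is 2(1 − Φ(1.96/√DE)): 5.3%, 6.6%, 8.2% and 11.5% at ICC 0.01, 0.05, 0.10 and 0.20. Simulation with no arm effect (100,000 trials per setting) gives, near-equal / uneven:

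| ICC | DE | Resident t-test | Wilcoxon, read as rank-sum |
|---|---|---|---|
| 0.01 | 1.03 / 1.04 | 5.3% / 5.5% | 5.0% / 5.2% |
| 0.05 | 1.14 / 1.22 | 6.5% / 7.5% | 6.2% / 7.1% |
| 0.10 | 1.27 / 1.43 | 8.4% / 10.3% | 7.9% / 9.7% |
| 0.20 | 1.55 / 1.86 | 11.8% / 15.4% | 11.1% / 14.6% |

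At ICC 0 the t-test gives 5.0%. A separate simulation with equal sizes gave 6.3%, 8.4% and 11.7% at ICC 0.05, 0.10 and 0.20.

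For the four-category change the outcome split must also be assumed. With 70/10/10/10% and ICC 0.05 (60,000 trials), chi-square gives 6.2% / 7.4% and Fisher's test 7.3% / 8.4%. Not every test inflates: Fisher's test on a single binary outcome with a 20% event rate stays at 3.0% / 3.6% at ICC 0.05.

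**Detectable difference.** With 13 df (15 − 2), the noncentral t multiplier is 3.031. At ICC 0 this gives 3.031 × 0.632 × √(2/28) = 0.512 SD. Multiplying by √DE:

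| ICC | Near-equal | CV 0.65 |
|---|---|---|
| 0.05 | 0.546 SD | 0.565 SD |
| 0.10 | 0.578 SD | 0.613 SD |
| 0.20 | 0.637 SD | 0.699 SD |

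The value reaches 0.66 when DE = (0.66/0.512)² = 1.66. That is ICC 0.66/2.73 = 0.24 (near-equal) or 0.66/4.31 = 0.15 (CV 0.65).

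**If there were one building per arm**, with 28 residents each, building-level df would be 0. The resident t-test would then have 8.2% error at ICC 0.01 and 20.9% at 0.05.

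**The case against.** The strongest reply is that the size of the problem is not established.

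- **ICC.** The relevant ICC is that of change, so stable differences between buildings cancel. A single research nurse delivers the intervention, which removes one source of variation between buildings. Table 2 speaks of recommending changes to buildings, not of making them. An effect shared by all treated buildings is treatment effect, not clustering. With fewer than four completers per building, the excess at ICC 0.01 is only 0.3 to 0.5 points.
- **Purpose.** The study is sized for feasibility, and its only stated success rule, at least 75% of checklist items, uses no p-value.
- **Power.** Clustering does not by itself overturn 0.66 SD. With the plan's rounded SD of 0.6, the base is 3.031 × 0.6 × √(2/28) = 0.486 SD, and 0.66 is reached only at ICC about 0.31 or 0.20.
- **Remedy.** A mixed model with 13 df is itself conservative: about 3% at ICC 0.01 and 3.6% to 3.7% at 0.05.
- **Dichotomous tests.** Table 3 names no clearly dichotomous outcome, so those figures are illustrative.

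All of this is fair, and it limits the weight of the point. It does not remove the mismatch. The plan names co-primary outcomes, specifies between-group tests and claims 80% power at a 5% level. Having chosen to test, it needs an error term that matches the randomization. The direction of the t-test error is the same for any positive ICC. The remedy's conservatism is a cost to disclose, and alternatives that hold close to 5% are available.

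**Conclusion.** The concern holds and should be fixed. As written, the co-primary comparison leaves building variation out of its error term. The excess over 5% is slight at ICC 0.01 and clear from about 0.05. The highest t-test figure, 15.4%, needs both ICC 0.20 and uneven building sizes. These figures rest on an assumed ICC, assumed building sizes, 56 completers and 15 buildings.

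The estimated mean difference, the resident-level SD and the feasibility criterion are not materially affected. Clustering does not refute the stated 0.66 SD at small ICC. The conflict between one site per arm and 15 buildings must be settled first, because the degrees of freedom of any correct analysis depend on it.

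**What to change.** 1. In Outcome measures and Waitlist control, reconcile the wording with the 15 buildings of Aim 3.
2. In the analysis plan, replace the resident-level tests with one pre-specified analysis by randomized building. For continuous change, use a linear mixed model (REML) with arm as fixed effect, a random building intercept and a t reference with df equal to buildings analysed minus 2 (13 if all 15 contribute). Acceptable alternatives are a t-test on building means, if sizes are similar, or a permutation test that re-randomizes buildings. Choose one before the data are seen.
3. For any dichotomous outcome, use the building permutation test with the Pearson chi-square as its statistic. An unstratified 8 against 7 split has 6,435 allocations; otherwise follow the actual randomization scheme.
4. Report the ICC of change with an interval, and say that it will be imprecise. At a true ICC of 0.05, the central 95% of simulated estimates ran from about −0.18 to 0.31 with near-equal sizes.
5. In the power text, restate the detectable difference over an assumed ICC range, with building-level df and the design effect 1 + ((1 + CV²)m − 1) × ICC.

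**Cost.** Wording and a little analysis time; no extra residents or data. Intervals widen slightly. In simulation over ICC 0 to 0.20, the mixed model's type I error was 2.9% to 5.5%, lowest when the ICC is near zero. Building means held 4.5% to 5.0%, but lose power when sizes are uneven: 68% against 79% for the mixed model at ICC 0.05. At ICC 0.05 and 0.20, permutation held 5.1% to 5.3% for continuous change and 4.8% to 5.1% for the four-category change.
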